#### 6.A.2 *Secondary efficacy criteria*

##### 6.A.2.1. Number of hospital days due to severe COPD exacerbation

On the basis of the reasons for admission of each hospitalisation during the *Follow-Up Period*, as reported by the investigators in the e-CRF, the number of hospital days due to severe COPD exacerbation will also be calculated for each randomised patient.

##### 6.A.2.2. Number of moderate and severe COPD exacerbations

Each time the patients experiment a COPD exacerbation throughout the study, the investigators will record the following information in the e-CRF:

- Date of diagnosis,
- Medication prescribed for treating the exacerbation (*name, dosage and duration*),
- Dates of admission and discharge from hospital, if applicable.

**Moderate COPD exacerbations** will be defined as exacerbation of symptoms not requiring hospitalisation but ending with a prescription of antibiotics and/or systemic corticosteroids.

**Severe COPD exacerbations** will be defined as exacerbation of symptoms requiring hospitalisation and/or leading to death . In the subgroup of patients experiencing at least one severe COPD exacerbation during their *Follow-Up Period*, the time elapsed between Visit 1 and the date of the first severe COPD exacerbation (*defined by either the date of hospital admission or the date of death*) will be described as the time to first severe COPD exacerbation (*expressed in number of days elapsed since Visit 1*).

A new episode of moderate/severe COPD exacerbation will be counted when patients have been off systemic corticosteroids and/or antibiotics for at least 14 days following their previous exacerbation .

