### 3.C EXCLUSION CRITERIA

If any of the exclusion criteria are fulfilled, potential patients are not eligible for study participation. The criteria for exclusion are:

- 9) Patient previously randomised in the study,
- 10) Patient on LTOT for another reason than COPD, *e.g.,* for a concomitant significant chronic disease such as asthma, diffuse bronchiectasis including cystic fibrosis, sarcoidosis, lung fibrosis, kyphoskoliosis, neuromuscular disease, severe left chronic cardiac failure, ...,

- 11) Patient with limited probability of survival (< 6 months),
- 12) Patient with a tracheostomy,
- 13) Patient receiving long term oral corticosteroids therapy (*defined as continuous use of > 10 mg of prednisone or equivalent per day for more than 6 weeks. Successive courses of oral corticosteroids separated by a period of less than 7 days will be considered as continuous use*),
- 14) Patient who has, in the knowledge of the investigator, a condition which could limit compliance to study procedures, such as:
  - 14.a) Alcohol abuse,
  - 14.b) Drug (*e.g., cannabis, cocaine, ...*) abuse,
  - 14.c) Solvent abuse,
  - 14.d) Dementia,
  - 14.e) Uncontrolled psychiatric illness,
- 15) Patient not covered by a health insurance,
- 16) Patient living in a medicalised nursing home,
- 17) Patient who participated in another interventional clinical trial within 30 days before Selection.

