### **5.D.1**     *Allowed medications*

All COPD and non-COPD medications which are deemed necessary by the investigator for the patient's welfare may be administered at any time at the investigator's discretion. They will be recorded accordingly in the e-CRF.

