### **5.D.2**     *Not permitted medications*

Long term oral corticosteroids therapy is not permitted at Selection. Long term use is defined as continuous use of > 10 mg of prednisone or equivalent per day for more than 6 weeks. Successive courses of oral corticosteroids separated by a period of less than 7 days will be considered as continuous use.

However, if during the study *Follow-Up Period*, a patient requires such a therapy, he/she will not be withdrawn from the trial but the corresponding data must be recorded by the investigator in the e-CRF.

The patients will not be allowed to participate to any other interventional study during their participation to this trial.

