## **ADDITIONAL ANALYSES OF THE PRIMARY EFFICACY CRITERION**

To further explore the primary criterion, a parametric analysis of variance of the primary efficacy criterion will be performed on the ITT data set including three (3) factors: study group and country effects, as well as their interaction.

The primary analysis of the primary efficacy criterion and its supportive analyses will be repeated on the duration of unscheduled hospitalisations whatever their reason, confirmed in a blind manner by the members of the EVC (*see section 6.D*).

An exploratory multiple-factor regression analysis will also be performed to identify the independent predictors of the primary efficacy criterion. The statistical model building will follow the principle of seeking the most parsimonious model which still explains the data. The clinically relevant factors which will be investigated will be:

- study group,
- gender,
- age classified in the six (6) categories pre-defined in the Charlson Comorbidity Index (*i.e.*, < 50, [50 ; 60[, [60 ; 70[, [70 ; 80[, [80 ; 90[ and [90 ; 100[ years old),
- smoking status at Visit 1,
- need for respiratory assistance (*i.e.* oxygen and/or home Non-Invasive Ventilation (NIV) at Selection (Visit 0),
- need for Continuous Positive Airway Pressure (CPAP) at Selection (Visit 0)),
- need for respiratory assistance (*i.e.*, oxygen therapy and/or home Non-Invasive Ventilation (NIV)) at Selection (Visit 0) and/or during the study participation,
- need for Continuous Positive Airway Pressure (CPAP) at Selection (Visit 0) and/or during the study participation,
- need for continuous Long Term Oxygen Therapy (*i.e.*, daily oxygen duration prescribed of 15 hours or more) at Selection (Visit 0) and/or during the study participation,
- experience of at least 2 moderate or severe COPD exacerbations during the *Follow-Up Period* as recorded by the investigators,
- baseline FEV1 value (*expressed as percentage of predicted value*) classified in the four (4) categories pre-defined in the BODE index (*i.e.*, ≤ 35, ]35 ; 50[, [50 ; 65[ and ≥ 65%),
- Body Mass Index (BMI) at Selection classified in the two (2) categories pre-defined in the BODE index (*i.e.*, ≤ 21 and > 21 kg/m^2),
- baseline BODE index classified in the four (4) categories mentioned in section 6.A.2.6 (*i.e.*, [0 ; 2], [3 ; 4], [5 ; 6] and [7 ; 10]),

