## **ANALYSES OF THE SECONDARY EFFICACY CRITERIA**

All analyses of the secondary efficacy criteria will be performed on the ITT data set (*defined in section 7.B.3.1*).

**The number of hospital days due to severe COPD exacerbations** will be analysed in exactly the same way as the primary efficacy criterion, including its primary, supportive and additional analyses previously described.

**The number of moderate and severe COPD exacerbations** separately as recorded by the investigators will be compared between both study groups with the Wilcoxon's rank sum test, in all countries pooled together.

**Time to first severe COPD exacerbation** (*expressed in number of days*) throughout the *Follow-Up Period* will be tabulated by study group, as quantitative data, in the subgroup of patients from the ITT data set experiencing at least one severe COPD exacerbation during their *Follow-Up Period*, as reported by the investigators, in all countries pooled together. Moreover, time to first severe COPD exacerbation throughout the *Follow-Up Period* will be described globally by study group, on the ITT data set, using Kaplan-Meier's estimates to display the probability of survival and of experiencing severe COPD exacerbation. Survival times will be censored at the earliest time of occurrence of the following events:

- the patients' last contact (*this will apply to the subgroup of patients who never experience any severe COPD exacerbation and who are never hospitalised for any reason during their Follow-Up Period*),
- the time to first severe COPD exacerbation (*for the subgroup of patients experiencing at least one severe COPD exacerbation during their Follow-Up Period*),
- the time to first hospital admission for another reason than COPD exacerbation (*for the subgroup of patients hospitalised at least once during their Follow-Up Period*),
- the time to death for another reason than COPD exacerbation, if applicable.

If relevant, time to first severe COPD exacerbation will be compared between both study groups with the Log rank test.

**The use of health care services due to COPD and to all causes** separately will be tabulated by study group and type or unit of time (*i.e., qualitatively in terms of volume without being priced*). Each category separately will be compared between both study groups using either the Student's t test or the Wilcoxon's rank sum test depending on their distribution.

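### The rule for counting a new exacerbation (6.A.2.2) does not separate exacerbation courses from maintenance steroids or antibiotics, so read literally it caps the count in eligible patients on such treatment

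*Protocol*

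**What the plan says.** Protocol 6.A.2.2 defines a moderate exacerbation as "exacerbation of symptoms not requiring hospitalisation but ending with a prescription of antibiotics and/or systemic corticosteroids", and a severe one as requiring hospitalisation and/or leading to death. Successive episodes are separated by this rule: "A new episode of moderate/severe COPD exacerbation will be counted when patients have been off systemic corticosteroids and/or antibiotics for at least 14 days". The sentence goes on to place that interval after the previous exacerbation.

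Three other places decide who can be on these drugs:

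- **3.C, criterion 13** excludes long-term oral corticosteroids, defined as "continuous use of > 10 mg of prednisone or equivalent per day for more than 6 weeks". Continuous use at 10 mg/day or less is therefore eligible.
- **5.D.1** permits at any time "All COPD and non-COPD medications which are deemed necessary by the investigator". Neither 3.C nor 5.D.2 restricts antibiotics.
- **5.D.2** applies the steroid restriction at Selection only. If a patient needs such therapy during Follow-Up, "he/she will not be withdrawn from the trial but the corresponding data must be recorded".

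The counts are used twice in 7.B.3.5. The numbers of moderate and of severe exacerbations "separately as recorded by the investigators will be compared between both study groups with the Wilcoxon's rank sum test". The list of candidate predictors for the exploratory regression on the primary criterion also includes "experience of at least 2 moderate or severe COPD exacerbations during the" Follow-Up Period.

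**The concern.** A washout rule is meant to stop one exacerbation, or its relapse, from being counted twice. It works if being off the drug marks the end of treatment for the previous episode. In a patient on daily low-dose prednisone or a long-term antibiotic it marks nothing, because that patient is never off the drug. Later exacerbations then fail the rule however far apart they are, even when each leads to an admission.

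At stake is the meaning of a listed secondary criterion. The trial is open (4.B.2), and in the Intervention group a confirmed alarm prompts a treatment decision by the investigator (Appendix 2). Maintenance prescribing after randomisation could therefore differ between groups. If it did, the group with more of it would record fewer exacerbations because of the counting rule alone.

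**Working it through.** **Plan's own figures.** The protocol gives no exacerbation rate and no share of patients on maintenance treatment, so there is no figure to reproduce on this point. The sample size in 7.B.2 rests on hospital days (difference 10, SD 25), and no exacerbation count enters it.

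**Rule applied to the patients whom the protocol allows**

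| Patient | Allowed by | Days off after the previous episode | Result under 6.A.2.2 as worded |
|---|---|---|---|
| Treated only with courses for exacerbations | – | Can reach 14 | Later episodes can count |
| Continuous prednisone, 10 mg/day or less | 3.C (13) | 0 | At most 1 episode |
| Continuous antibiotic | 5.D.1, no restriction | 0 | At most 1 episode |
| Starts long-term steroid in Follow-Up | 5.D.2 | 0 after the start | At most 1 more after the start |

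In the last row, one further episode can count because the 14 days may have been completed before maintenance treatment began. After that episode the patient is never off the drug.

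Two consequences follow:

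- A patient on maintenance treatment throughout can never meet the regression factor for two or more exacerbations, whatever the true rate.
- Two secondary criteria can disagree. Hospital days for severe exacerbation (6.A.2.1) come from the recorded reasons for admission, with no washout. Three exacerbation admissions in a patient on daily low-dose prednisone would contribute three stays of hospital days but only one severe exacerbation.

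**Illustration of the loss within one affected patient.** Every input here is an assumption except the 14 days: exacerbations follow a Poisson process at r per year, courses last 10 days, follow-up is 365 days, and maintenance treatment runs throughout. An episode then counts only if at least 10 + 14 = 24 days have passed since the last one. With q = exp(−24r/365):

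- not on maintenance: expected count = (1 − q) + r × (341/365) × q
- on maintenance: expected count = P(at least one event) = 1 − exp(−r)

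| r per year | q | Not on maintenance | On maintenance | Shortfall |
|---|---|---|---|---|
| 1 | 0.936 | 0.94 | 0.63 | 33% |
| 2 | 0.877 | 1.76 | 0.86 | 51% |
| 3 | 0.821 | 2.48 | 0.95 | 62% |
| 4 | 0.769 | 3.10 | 0.98 | 68% |

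For r = 2: (1 − 0.877) + 2 × 0.934 × 0.877 = 1.76, and 1 − exp(−2) = 0.86. A simulation under the same assumptions agrees to within 0.01.

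The effect on the trial is the shortfall multiplied by the share of patients affected. The documents do not give that share, so the calculation stops here.

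**The case against.** **The intent is probably the exacerbation course.** The same section has the investigator record the medication prescribed for each exacerbation, with its duration. The rule also refers to the interval after the previous exacerbation. This reading is plausible and is what the fix below would write down. It is not what the sentence says, and about 45 centres in four countries have to apply it.

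**The and/or could mean off either class.** A patient on maintenance prednisone could then qualify by being off antibiotics. But anyone treated with one class only would always be off the other, so the rule would separate almost nothing. That reading needs correcting too.

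**The cap depends on mechanical application.** Counts are analysed as recorded by the investigators, and no program is stated to discard a second admission. This is fair, and the actual loss may be smaller than the literal one. But the definition is already written in the protocol, so this is not a detail merely left to the analysis plan.

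**Long-term antibiotics are inferred.** The protocol never mentions prophylactic antibiotics. Their admissibility follows only from the general permission in 5.D.1 and the absence of a restriction.

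**Stronger readings that a reader might infer, and that are not supported:**

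- *That the treatment comparison is biased by a known amount.* If a pooled mean of 2.5 exacerbations a year is assumed (negative binomial, shape 2), capping at one loses 68% of an affected patient's events. With 5% of one group and 15% of the other affected, the ratio of means is 0.93 with no true effect. But the split and the rate have no source in the protocol. The planned test is a Wilcoxon on each type separately, not a ratio of pooled means. Patients who start maintenance mid-study are not capped from day 0. The 68% also ignores the merging of close episodes that the rule causes in everyone.
- *That the main result is at risk.* Unscheduled hospital days do not use the new-episode rule, and 7.B declares all other analyses exploratory and descriptive.
- *That baseline severity is distorted.* The prior-year count in 4.B.1.2 cites the same definitions. But it is patient-reported and taken before randomisation, and eligibility needs only one hospitalised exacerbation.

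**Conclusion.** The point holds as a defect in a written endpoint definition. As worded, the rule does not distinguish exacerbation courses from maintenance treatment, and the protocol admits or keeps patients on such treatment. The cap is certain on the literal reading for continuous steroid use. For antibiotics it also rests on the inference from silence.

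The reach is limited to the exploratory secondary counts of moderate and severe exacerbations and one candidate factor in an exploratory regression. Hospital days for severe exacerbation come from admission records. Time to first severe exacerbation is dated by admission or death, not by the new-episode rule.

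The loss within an affected patient could be large (33% to 68% at assumed rates of 1 to 4 per year). The effect on the trial cannot be sized and could be negligible if few patients are on maintenance treatment. It should be corrected, but it does not threaten the primary conclusion.

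**What to change.** Amend the new-episode sentence in 6.A.2.2 to say that:

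- the 14-day interval runs from the end of the systemic corticosteroid and/or antibiotic course prescribed for the previous exacerbation, or from the return to the patient's earlier maintenance regimen;
- maintenance corticosteroids or antibiotics are not counted as exacerbation treatment.

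This changes how episodes are counted, not how patients are treated. The cost is one sentence and the matching derivation. No new data are needed: 6.A.2.2 already collects the name, dosage and duration of each exacerbation treatment, and 5.D collects start and end dates and the reason for every pharmaceutical therapy.

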#### 6.A.2.3. Use of health care services due to COPD and to all causes

**The investigators** will record the following information about use of health care services during the *Follow-Up Period*:

- For each medical or paramedical consultation: date, type of visit (*home versus out-patient visit*), category of health care provider consulted (*specialist physician, primary care physician, nurse, respiratory therapist, ...*) and the reason for consulting,
- Home hospitalisation: start and end dates.

**The health counsellors** will record the following information about use of health care services during the *Follow-Up Period* (*for the Intervention group only*):

- For each unscheduled phone call (*on patient's request or because of the symptom scoring*): date, duration of the phone call and the reason for calling.

If any of the use of health care services recorded are the results of an AE or SAE, then the appropriate e-CRF should also be completed by the investigator.

#### 6.A.2.4. Health-related quality of life

Quality of life will be assessed for each randomised patient every 6 months (*corresponding to Visits 1, 3 and 5*) using the self-administered COPD-specific version of the St George's Respiratory Questionnaire (*SGRQ-C*)  and the 15D health-related quality of life instrument (<http://www.15d-instrument.net>), in their linguistically validated versions for the 4 study countries. Time to complete each questionnaire is about 10 minutes for SGRQ-C and 5-10 minutes for 15D.

- The SGRQ-C (*sample provided in Appendix 3*) is a disease-specific questionnaire designed to measure the impact of respiratory disease on overall health, daily life, and perceived well-being. It has been developed for use by patients with asthma and COPD. The questionnaire is composed of 14 questions grouped in 2 sections: 'Symptoms' (*questions 1 to 7, which address the frequency of respiratory symptoms*) and 'Activity and Impacts' (*questions 8 to 14, which address the patient's current state in terms of disturbances to daily physical activity and psycho-social function*). Each questionnaire response has a unique empirically derived weight, ranging from 0 to 100, the highest scores indicating poorer health status. The total score and the three (3) component subscores will be calculated (*symptoms, activity and impacts*) by using the scoring algorithm manual provided by the SGRQ-C owner. A mean change score of 4 units is associated with a slightly efficacious treatment, 8 units with a moderately efficacious treatment and 12 units with a very efficacious treatment .

- The 15D (*sample provided in Appendix 3*) is a generic, comprehensive (*15-dimensional*), self-administered instrument for measuring present health status in adults and for estimating cost-effectiveness of interventions. It is composed of 15 questions (*mobility, vision, hearing, breathing, sleeping, eating, speech, elimination, usual activities, mental function, discomfort and symptoms, depression, distress, vitality and sexual activity*) with 5 alternative responses to each question. A set of utility weights will be used to score the patient's responses and to generate the 15D score (*single index number*) on a 0-1 scale, where a score of 1 represents a perfect state. The 15D has been already used as a utility measure in COPD .

#### 6.A.2.5. Physiological parameters

Results of the following medical evaluations will be recorded for each randomised patient at Visits 1 and 5:

- Pulmonary function tests, performed according to ATS/ERS guidelines , and including:
  - Spirometry: for measurements of Forced Expiratory Volume in one second (FEV1), Forced Vital Capacity (FVC), Forced Expiratory Flow between 25% and 75% of the vital capacity (FEF25-75), Inspiratory Capacity (IC), and the FEV1/FVC ratio.

The values reported by the investigator will be post-bronchodilator values in absolute values and percentage of predicted values in force in the investigational centre.

- Six-Minute Walk Test (6MWT) on room air or on oxygen for patients on oxygen therapy, performed according to ATS/ERS guidelines . The investigator will report *i*) the six-minute walking distance (*in meters*) (*the percentage of predicted value based on age, height, weight and sex*  will be calculated by the *e-CRF*), *ii*) the SpO2 value at rest before starting the 6MWT, *iii*) the minimum SpO2 value recorded during the 6MWT, *iv*) the pulse rate value at rest before starting the 6MWT, *v*) the maximum pulse rate value recorded during the 6MWT (*the percentage of maximum theoretical heart rate will be calculated by the e-CRF*) , *vi*) the reason for premature ending of the 6MWT, and the number of minutes walked before discontinuation, if applicable, and *vii*) the oxygen flow rate(s) delivered during the 6MWT, if applicable.

- Transthoracic Doppler echocardiography. The investigator will report *i*) the estimated Pulmonary Artery Systolic Pressure (PASP), derived from tricuspid regurgitation and expressed in mmHg (*a PASP of 35 mmHg and above will be considered as the cut-off value for pulmonary hypertension*), *ii*) the left ventricular Ejection Fraction (EF), as a parameter of systolic left heart function, expressed in percentage (*a EF of 50% and below will be considered as the cut-off value for systolic left heart dysfunction*) and *iii*) parameters to estimate and quantify diastolic left heart function, derived from the transmitral flow: deceleration time of the early transmitral flow (*expressed in milliseconds*), peak velocity of the early transmitral flow (*E-wave, representing the early filling phase, expressed in cm/sec*), peak velocity of the late transmitral flow (*A-wave, representing the atrial contraction, expressed in cm/sec*). Ratio of the peak velocity of the E-wave to the A-wave will be calculated by the e-CRF. It is expected that these measurements will not be possible in a number of patients, approximately estimated to one third, because of technical limitations due to chest wall configuration.

